6.5 Data presentations

The data will be summarised in tabular form by treatment group apart from disposition of patients, protocol deviations, 'background and demographic' data and adverse events which will be summarised by treatment group and overall patients. Treatment labels will be "1000 mg DS102 (BD)", "Placebo (BD)" and "All Patients" (where applicable).

Only scheduled post-baseline laboratory, electrocardiogram (ECG), nutritional status assessment, cytokeratin18-M30/M65 and vital signs values will be tabulated, post-baseline repeat/unscheduled assessments will be disregarded, although they will be listed and in particular all clinically significant values will be noted (where applicable).

Analysis sets will be summarised using the enrolled set. Study completion/withdrawal and protocol deviations will be summarised using the RAN set. Background and demographic characteristics will be summarised using the FAS. The primary efficacy endpoint will be summarised using the FAS and the PPS. Secondary endpoints will be based on the FAS only. Prior/concomitant medications, administration of study treatment and exposure and safety will be summarised using the SAF. PK (double-blind phase) will be summarised using the PK (double-blind phase) set.

PK (pilot phase) will be based on the PK (pilot phase) set, PK (double-blind phase) will be based on the PK (double-blind phase), safety listings will be based on the SAF set, and all other listings will be based on the enrolled set.

Listings will be sorted by phase, treatment group, patient number and date/time of assessment.

Treatment groups will be presented in the following order “Pilot phase: 1000 mg DS102 (BD)”, “Double-blind phase: 1000 mg DS102 (BD)” and “Placebo (BD)”.

Graphical presentations of the data will also be provided where appropriate.

6.6 Disposition of patients

The number and percentage of all patients enrolled, included in the RAN, FAS, PPS, SAF and PK (double-blind phase) analysis sets, who completed the study and prematurely discontinued the study, study duration and treatment duration, will be summarised. The number and percentage of patients will be summarised by their reasons for withdrawal from the study and study treatment. Study duration for each patient will be derived as the number of days between date of randomisation and the date of study completion or the date of early study withdrawal. Treatment duration will be derived as the number of days between 1st administration of study drug and the date of the last administration of study drug.

Eligibility for each of the analysis sets along with reasons for exclusion will be listed. Study completion/withdrawal data will be listed. Consent and visit dates will be listed. Randomisation details will be listed.

Analysis sets presented will be the ones defined in this SAP.

6.7 Protocol Deviations

Prior to database lock, Afimmune will review the individual deviations and classify them as major (which includes those described in section 6.3 above) or minor during a BDRM.

Details of all protocol deviations (date, deviation category, specific details and classification of major or minor) and patient eligibility will be listed.

The number and percentage of patients with at least one major protocol deviation will be summarised. Major protocol deviations will be summarised for each major deviation category.

6.8 Background and Demographic Characteristics

6.8.1 Demography

Demographic characteristics (age, sex, ethnic origin and race), body measurements (height, weight, body mass index (BMI)), alcoholic hepatitis duration, average weekly consumption of alcohol (units per week) and the presence of a history of alcohol abuse for > 6 months (Yes/No) will be summarised by treatment group and overall.

Age at informed consent is captured on the electronic case report form (eCRF).

BMI is calculated as (weight (kg)/height (m)²).

Date of alcoholic hepatitis diagnosis will be recorded. Alcoholic hepatitis duration will be calculated in years as [date of informed consent - date of alcoholic hepatitis

diagnosis+1]/365. Dates will be imputed according to this rule: if the day is missing, day will be imputed as 1st day of the month, if the month is missing, month will be imputed as 1st month of the year.

All patient demographic data including informed consent, AH diagnosis and substance use data will be listed.

6.8.2 Medical History

Medical history events will be coded using the latest Medical Dictionary for Regulatory Activities (MedDRA) dictionary version. The version used will be indicated in the data summaries and listings. The number and percentage of patients will be presented for ongoing conditions and previous conditions separately by system organ class (SOC), and preferred term (PT), where SOC and PT will be presented in decreasing frequency of the total number of patients with medical history events. All events will be listed.

6.8.3 HIV, Hepatitis B and Hepatitis C screening

Details of the screen for human immunodeficiency virus (HIV), hepatitis B and hepatitis C will be listed.

6.8.4 Liver Ultrasound

Liver ultrasound data will be summarized and listed.

6.9 Prior and Concomitant Medications

Medications will be coded using the latest World Health Organization Drug dictionary (WHO Drug) version. The version used will be indicated in the data summaries and listings.

Prior medications are defined as those that started and ended prior to the first administration of study treatment. Medications that are ongoing at the first administration of study treatment or started after time of first administration will be deemed to be concomitant medications. If medication dates are incomplete and it is not clear whether the medication was concomitant, it will be assumed to be concomitant.

The number and percentage of patients taking prior and separately concomitant medications will be summarised by medication class and standardised medication name, where medication class and standardised medication name will be presented in decreasing frequency of the total number of patients with medications. In summary tables, patients taking multiple medications in the same medication class or having the same standardised medication recorded multiple times in the study will be counted only once for that specific medication class and standardised medication name.

Medication data will be listed, and concomitant medications will be flagged.

6.10 Administration of Study Treatment and Compliance

The number of doses of study treatment administered will be derived as the (total number of study drug capsules dispensed – total number of study drug capsules returned) over all visits.

Patients compliance with treatment will be measured by the information captured on the patient diary card.

Overall treatment compliance will be derived as a percentage as the (number of doses of study treatment recorded as being administered/N) *100.

Where N= the number of times the patient should have received study treatment= (Date of treatment withdrawal or day 28/early termination visit – date of baseline visit + 1) x 2

Number of doses of study treatment administered and overall treatment compliance will be summarised.

Study drug dispensing, study drug return and diary card data will be listed.

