### **8.2.2 Treatment Period**

Following completion of a successful screening visit, patients will begin the comparative treatment period (28 days).

At the start of the comparative treatment period, after confirmation of continued eligibility, patients will be randomly assigned to one of the two treatment regimens.

Patients will take the allocated investigational medicinal product (IMP) to which he/she is allocated twice-daily, in the morning and in the evening, within 30 minutes after a meal, throughout the comparative treatment period. Each administration of IMP will be recorded in the eCRF/hospital records or in a patient diary card, if discharged before day 28 of the study.

Patients who discontinue the study early will have all study procedures scheduled for Visit 8 (see Section 8.2.9) performed as soon as possible after patient withdrawal so that all study-related information can be recorded.

Counselling on alcohol consumption should be performed during the study. In-study and post-discharge referral and intervention will be provided as needed.

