### **8.2.9 Visit 8/Day 28/Early Termination**

The following assessments will be performed:

- Physical examination (as detailed in Section 9.2.2)
- Vital signs (blood pressure, heart rate and body temperature), as detailed in Section 9.2.4);
- ECG (as detailed in Section 9.2.3)
- Pharmacokinetic sampling (as detailed in Section 9.2.8.1)
- Exploratory blood sampling (as detailed in Section 9.2.8.2)
- Samples for clinical laboratory safety tests (haematology, serum biochemistry, and coagulation tests as detailed in Section 9.2.5)
- Pregnancy test (as detailed in Section 9.2.7)
- MELD (as detailed in Section 9.1.1)
- MDF (as detailed in Section 9.1.7)
- m-SOFA (as detailed in Section 9.1.8)
- APACHE II score (as detailed in Section 9.1.9)
- Total bilirubin (as detailed in Section 9.1.2)
- CK-18 (as detailed in Section 9.1.6)
- AST:ALT (as detailed in Section 9.1.3)
- Child pugh score (as detailed in Section 9.1.5)

- Gamma GT (as detailed in Section 9.1.4)
- Biomarker (as detailed in Section 9.2.8.3)
- West Haven criteria assessment (as detailed in Section 9.1.11)
- Lille score assessment (as detailed in Section 9.1.10)
- Collection of acute kidney injury, ascites and variceal haemorrhage data
- AE assessment (as detailed in Section 11)
- Concomitant medication assessment (as detailed in Section 9.2.10)

In addition, the following assessments of nutritional status will also be performed, with nutritional interventions provided where required:

- BMI
- Bedside Subjective Global Assessment (SGA) score (0, 1, 2, and 3). Patients will be classified into the following categories:
  - Well nourished (0)
  - Mild malnutrition (1)
  - Moderate malnutrition (2)
  - Severe malnutrition (3)

The IMP or placebo will be returned. Further IMP or placebo will not be supplied to the patient.

On completion of this visit, patients will be advised that they will be required to return to the investigational site in 62 days at Visit 9 for final assessment.

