#### **9.2.8.1 Pharmacokinetic sampling**

Blood samples for pharmacokinetic (PK) analysis will be collected via direct venepuncture as per the Study Flow Chart (Appendix 1 and 2) at Visit 2/Baseline, Visit 3/Day 3, Visit 4/Day 5, Visit 5/Day 7, Visit 6/Day 14, Visit 7/Day 21, and Visit 8/Day 28/Early Termination.

Trough plasma samples will be obtained from all patients (pilot and double blind phases) prior to first daily dose on the indicated days. Additional post-dose serial plasma samples will be obtained from the six patients on Days 0 and 7 of the preceding pilot phase for full PK characterisation at 0.5, 1, 2, 3, 4, 6, 7, 8, 10, and 12 (before next dose) hours post-dose.

A 1 mL blood sample will be taken at each time point. Following centrifugation, plasma samples will be split in two and a back-up sample will be handled as specified in Section 9.2.12 and described in the laboratory manual.

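### SAP 6.10 reports capsules as doses, counts the end visit as a full dosing day, and leaves the source of the compliance figure unclear

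*SAP*

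**What the plan says.** SAP 6.10 sets out two derived quantities and a data source.

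- Exposure: "The number of doses of study treatment administered will be derived as the (total number of study drug capsules dispensed", minus the capsules returned, over all visits. Nothing is divided by two.
- Compliance: "number of doses of study treatment recorded as being administered/N", times 100. The denominator is introduced as "Where N= the number of times the patient should have received study treatment= (Date of treatment withdrawal or day 28/early termination visit"; from that date the baseline visit date is subtracted, one is added, and the result is doubled.
- Source: "Patients compliance with treatment will be measured by the information captured on the patient diary card". On listings: "Study drug dispensing, study drug return and diary card data will be listed".

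Both the dose count and the compliance percentage are to be summarised.

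The related text elsewhere is as follows.

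- SAP 4 and Protocol 10.2: two capsules twice daily, four a day. In SAP 6.4 the per-protocol rule treats three days of dosing as six doses.
- Protocol 8.2.3: two doses on Day 0.
- Protocol 10.3: 28 consecutive days of treatment.
- Protocol 10.2: the last dose falls on the day before the Day 28 or early termination visit. It labels that visit Visit 6, although Day 28 is Visit 8 in Protocol 8.2.9.
- Protocol 9.2.8.1, which includes Day 28 among the sampling days: "Trough plasma samples will be obtained from all patients (pilot and double blind phases) prior to first daily dose on the indicated days".
- Protocol 8.2.9, at the Day 28 visit: "The IMP or placebo will be returned. Further IMP or placebo will not be supplied to the patient".
- Protocol 8.2.2: each intake "will be recorded in the eCRF/hospital records or in a patient diary card, if discharged before day 28 of the study".
- Protocol Appendix 2: the Day 28 visit has a window of ±1 day.

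SAP 6.25 declares no departure from the protocol on any of these points.

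**The concern.** SAP 6.10 uses two units. The exposure count is in capsules but is called doses, while N counts intakes, two per day. The +1 in N suits a period whose last date is itself a full dosing day. The Day 28 visit is not one on any reading of the protocol, because drug is handed back there. The stated source, the diary card, does not exist for the part of treatment spent in hospital.

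At stake are the exposure table, the compliance table and, conditionally, membership of the Per-Protocol Set. Criterion 1 of that set in SAP 6.4 requires 80% of study treatment. It does not say how the 80% is derived, but 6.10 holds the SAP's only compliance definition.

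**Working it through.** **Capsules and doses.** A full course is 28 days × 4 capsules = 112 capsules, or 28 × 2 = 56 doses. The SAP 6.10 derivation gives 112 − 0 = 112 doses, twice the true number. Dividing by two gives 56.

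**Expected doses N.** First the protocol's own duration: two doses on Day 0 and the last dose on Day 27, the day before a nominal Day 28 visit, make 27 − 0 + 1 = 28 days. This agrees with Protocol 10.3 and gives 56 doses. SAP 6.10 gives N = (28 − 0 + 1) × 2 = 58, which implies 29 full days.

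The Day 28 trough in Protocol 9.2.8.1 can be read as implying a dose that day. Drug return at the visit leaves room for one such dose, not two. Across the visit window:

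| Visit on | N in SAP 6.10 | Doses if the last is the day before | Score | Doses with one on the visit day | Score |
|---|---|---|---|---|---|
| Day 27 | 56 | 54 | 96.4% | 55 | 98.2% |
| Day 28 | 58 | 56 | 96.6% | 57 | 98.3% |
| Day 29 | 60 | 58 | 96.7% | 59 | 98.3% |

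The excess is 2 on the first reading and 1 on the second, at every visit day in the window. On the first reading, visits on Day 27 and Day 29 give 27 and 29 dosing days, which does not fit the 28 days of Protocol 10.3. If 28 days held regardless, a Day 29 visit would give 56/60 = 93.3%.

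The +1 can be right on the other branch of the formula. If a patient stops treatment on Day 10 after both doses, N = (10 + 1) × 2 = 22, and Days 0 to 10 contain 22 doses. SAP 6.10 does not say which date applies when a patient has both a treatment-withdrawal date and a later early termination visit.

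**Per-protocol threshold, only if criterion 1 uses the 6.10 percentage.** At a nominal Day 28 visit:

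- 0.8 × 58 = 46.4, so 47 doses are needed.
- 0.8 × 56 = 44.8, so 45 doses are needed.
- 0.8 × 57 = 45.6, so 46 doses are needed.

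Patients whose status changes on the +1 alone:

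- 45 doses: 45/56 = 80.4%, but 45/58 = 77.6%.
- 46 doses: 46/56 = 82.1%, but 46/58 = 79.3%.
- On the 57-dose reading, only 46 doses: 46/57 = 80.7%, but 79.3% of 58.

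Patients with 45 or 46 of 56 doses have missed 11 or 10. Criterion 1 also excludes anyone who missed more than 6 doses in a row, whatever N is. The +1 therefore decides the matter only where the longest run of missed doses is 6 or fewer.

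**Source.** Protocol 8.2.2 divides the record: eCRF or hospital records, with the diary for patients discharged before Day 28. One sentence of SAP 6.10 points to the diary, and its listings name dispensing, return and diary data. The numerator, doses recorded as administered, is not confined to the diary. The text does not settle which records count.

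**The case against.** The best defence is that little depends on this. The factor of two is a unit label: it is constant, equal in both arms, and recoverable from the dispensing and return listings. Treatment duration is summarised separately (SAP 6.6). At a nominal Day 28 visit, full adherence is understated by 1.7 to 3.4 percentage points under the same formula in both arms. Allocation to analysis sets is decided at the blinded data review, which can also prompt a SAP amendment (SAP 6.2), and the per-protocol analysis is supportive. All of this stands and limits the importance of the point. It does not make the derivations right, and no other passage corrects them.

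Four stronger readings are tempting but not supported.

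- *That 57 is an upper limit on scheduled doses.* It holds only for a visit on nominal Day 28. With dosing to the day before, a Day 29 visit gives 58.
- *That inpatient doses will be dropped from compliance.* Read literally, and assuming the diary starts at discharge, a fully adherent patient with 7 inpatient days would score (56 − 14)/58 = 72.4%. The numerator's wording also admits hospital records, so this is an ambiguity to clear up rather than a shown error.
- *That compliance could reach 112/58 = 193%.* This requires the capsule count to be reused as the compliance numerator, which 6.10 does not say.
- *That the trial's main result is exposed.* The primary analysis uses the Full Analysis Set, which requires only randomisation and one dose.

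**Conclusion.** The two derivation errors hold as written, and the data source is unclear. A full course is summarised as 112 doses instead of 56. When the end date is the Day 28 or early termination visit, the visit day is wrongly counted as a full dosing day. At nominal Day 28, N is 58 against 56 or 57, so a fully adherent patient scores 96.6% or 98.3% and cannot reach 100%. Which of the two applies depends on how the protocol's passages on the last dosing day are reconciled; this review takes no position on that.

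The effect on the Per-Protocol Set is conditional on criterion 1 using the 6.10 percentage, and is confined to a narrow band near 80% among patients who also satisfy the consecutive-dose limit. The number of such patients cannot be computed from the documents. The Full Analysis Set primary analysis, alpha and power are unaffected. Severity: minor.

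**What to change.** In SAP 6.10:

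1. Define doses administered as (capsules dispensed − capsules returned)/2.
2. Reconcile Protocol 8.2.9, 9.2.8.1, 10.2 and 10.3 with SAP 6.10 on the last dosing day. Then define N as the intakes scheduled from the first dose to that day, without counting the visit day as a full dosing day.
3. Give one end-date rule for patients who stop early. Say whether the treatment-withdrawal date or the early termination visit date governs when both exist, and how intakes on the stop day count.
4. State that the compliance numerator uses eCRF or hospital records before discharge and the diary after it, and list both sources.

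In SAP 6.4, cite 6.10 as the source of the 80% in per-protocol criterion 1.

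The cost is SAP wording and one derivation change before database lock. Inpatient intakes held only in hospital notes may also have to be transcribed into the database.

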6.11 Primary Endpoint

The model for end-stage liver disease is employed in the evaluation of hepatic function and the assessment of prognosis. MELD is calculated based on variables including the international normalised ratio (INR), serum creatinine and serum bilirubin.

A MELD score ≥ 18 (within 24 hours of presentation) is considered a good predictor of 90-day mortality in patients with AH.

The efficacy primary endpoint of the study is the change in MELD score from baseline to day 28.

For the primary endpoint primary analysis; the null hypothesis ($H_0: \mu_1 = \mu_2$) of no difference in change from baseline to day 28 between those patients treated with 1000mg DS102 (BD) and placebo will be rejected in favour of the alternative hypothesis ($H_1: \mu_1 \neq \mu_2$) should the probability of the test statistic from observed data occurring if the null hypothesis were true (α) be less than 5%.

6.11.1 Primary Analysis

Percentage change in MELD score from baseline up to and including day 28 will be assessed by modelling change from baseline with a mixed-model repeated measures (MMRM) analysis, using the FAS, including terms for treatment group, visit, treatment-by-visit interaction as fixed effects and the baseline MELD value as a covariate. The adjusted treatment least squares (LS) means and adjusted mean LS difference between the active dose and placebo will be presented along with 95% confidence intervals (CI) and p-value for the day 28 timepoint. Early termination data will be entered into the model at the next scheduled visit following the date of termination, not at day 28.

F-tests from PROC MIXED will be based on Kenward-Roger's adjusted degrees of freedom. The following variance/covariance matrix structures for the repeated visits within a patient will be assessed: Compound symmetry, 1st order autoregressive, Toeplitz and unstructured. The variance/covariance matrix structure that results in the smallest Akaike's information criterion (AIC), indicating the best model fit will be selected.

Assumptions of normality will be assessed visually using diagnostic plots. Should assumptions of normality not hold the model will be fitted to the change from baseline of log-transformed data. Should the assumptions behind the model still not hold an alternative approach to the analysis will be decided following the BDRM and will be detailed in a SAP amendment.

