**PROTOCOL SYNOPSIS**

STUDY TITLE:	A Randomised, Double-Blind, Placebo-Controlled, Phase II Study to Assess the Efficacy and Safety of Orally Administered DS102 in Patients with Severe Acute Decompensated Alcoholic Hepatitis.
SHORT TITLE:	Efficacy and Safety of Orally Administered DS102 in Patients with Severe Acute Decompensated Alcoholic Hepatitis.
PHASE:	II
STUDY DURATION:	90 days (treatment duration: 28 days)
INVESTIGATIONAL PRODUCT:	DS102 Capsule Placebo (paraffin oil)
OBJECTIVES:	
Efficacy Objective:
 
 
• To compare the efficacy of orally administered DS102 capsules versus placebo, in the treatment of adult patients with severe acute decompensated Alcoholic Hepatitis (AH).
 
 
Safety Objective:
 
 
• To compare the safety of orally administered DS102 capsules versus placebo, in the treatment of adult patients with severe acute decompensated AH.
 
 
Pharmacokinetic Objective:
 
 
• To evaluate the pharmacokinetics (PK) of 15(S)-HEPE following orally administered DS102 capsules, in six adult patients with AH in the initial pilot phase of the study, followed by trough level assessment of 15(S)-HEPE in all study participants.
 

ENDPOINTS:	
Primary Endpoint
 
 
• % Change in MELD score from baseline to Day 28
 
 
Secondary Endpoints
 
 
• Change in total bilirubin from baseline to Day 7, 14, 21 and 28
 
• Proportion of patients showing a 25% reduction of bilirubin at day 7, 14, 21, and 28.
 
• Change in serum cytokeratin 18-M30/M65 from baseline to Day 7, 14, 21 and 28
 
• Change in AST levels from Baseline to Day 7, 14, 21 and 28
 
• Change in AST:ALT ratio from Baseline to Day 7, 14, 21, 28
 
• Change in MDF score from baseline to Day 7, 14, 21 and 28.
 
• Proportion of patients showing a 25% reduction in MELD score from baseline to Day 7, 14, 21 and 28
 
• Change in MELD score from baseline to Day 7, 14 and 21
 
• Change in modified Sequential Organ Failure Assessment (m-SOFA) from baseline to Day 7, 14, 21 and 28
 
• Proportion of patients with a 2-point worsening of m-SOFA
 

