## 5 STUDY ENDPOINTS

### 5.1 Primary Endpoint

- Percentage change in MELD score from baseline to Day 28

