## 12.3 Estimation of Sample Size

### Two-Sample T-Tests using Effect Size

#### Numeric Results for Two-Sample T-Test

Alternative Hypothesis: H1:  $d \neq 0$

Target Power	Actual Power	Effect Size				Alpha
		N1	N2	N	d	
0.80	0.8036	100	100	200	0.40	0.050
0.80	0.8002	90	90	180	0.42	0.050
0.80	0.8045	83	83	166	0.44	0.050
0.80	0.8044	76	76	152	0.46	0.050
0.80	0.8051	70	70	140	0.48	0.050
0.80	0.8015	64	64	128	0.50	0.050
0.80	0.8065	60	60	120	0.52	0.050
0.80	0.8014	55	55	110	0.54	0.050
0.80	0.8074	52	52	104	0.56	0.050
0.80	0.8030	48	48	96	0.58	0.050
0.80	0.8037	45	45	90	0.60	0.050

To discover an effect size of 0.54 (=Difference in means/standard deviation) in MELD change from baseline with 80% power, 55 patients per group are necessary under ideal assumptions using the t-test for independent samples (alpha=0.05, two-sided).

To take deviations from ideal parametric conditions and drop-outs into account randomisation of 60 patients per group is recommended.

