### **12.8.2 Primary Variables**

The primary efficacy variable will be change in MELD score from baseline to Day 28. This change in MELD score and its difference between treatment groups will be estimated using a General Linear Repeated Measures Model with treatment arm, baseline MELD value, visit and treatment arm by visit interaction as factors. The primary analysis will be based on the FAS and repeated for the PPS as a supportive analysis.

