2.2 Study Endpoints

The primary endpoint of the study is:

- Percentage change in Model End-stage Liver Disease (MELD) score from baseline to Day 28.

The secondary endpoints are:

- Change in total bilirubin from baseline to Day 7, 14, 21 and 28
- Proportion of patients showing a 25% reduction of bilirubin at day 7, 14, 21, and 28
- Change in serum Cytokeratin 18-M30/M65 from baseline to Day 7, 14, 21 and 28
- Change in Aspartate Transaminase (AST) levels from Baseline to Day 7, 14, 21 and 28
- Change in AST: Alanine Transaminase (ALT) ratio from Baseline to Day 7, 14, 21, 28
- Change in Maddrey Discriminant Function (MDF) score from baseline to Day 7, 14, 21 and 28

- Proportion of patients showing a 25% reduction in MELD score from baseline to Day 7, 14 and 21
- Change in MELD score from baseline to Day 7, 14 and 21
- Change in modified sequential organ failure assessment (m-SOFA) from baseline to Day 7, 14, 21 and 28
- Proportion of patients with a 2-point worsening of m-SOFA from baseline at Day 7, 14, 21 and 28
- Change in hepatic encephalopathy as assessed by West Haven criteria, from baseline at Day 7, 14, 21 and 28
- Incidence of acute kidney injury over 28 days (defined by requiring medicinal or mechanical support)
- Incidence of variceal haemorrhage, ascites or hepatic encephalopathy over 28 days

The exploratory endpoints are:

- Survival at day 7, 14, 21, 28 and 90 using Kaplan-Meier Plot
- Change in Gamma Glutamyl Transferase (GT) from baseline to Day 7, 14, 21 and 28
- Change in ALT from baseline to Day 7, 14, 21 and 28.
- Change in Child-Pugh score from baseline to Day 7, 14, 21 and 28
- Change in Acute Physiologic and Chronic Health Evaluation (APACHE) II score from baseline to Day 7, 14, 21 and 28
- Change in Lille score from baseline to Day 7, 14, 21 and 28

The safety endpoints are:

- Treatment emergent serious adverse events (SAEs), adverse events (AEs) and suspected unexpected serious adverse reactions (SUSARs)

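### The scale of the primary endpoint is inconsistent: percentage change in MELD is declared, change in MELD is hypothesised, and SAP 6.11.1 joins the two without a conversion

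*SAP*

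**What the plan says.** Three places declare the endpoint in percent. The synopsis puts a percent sign in front of "Change in MELD score from baseline to Day 28". Protocol 5.1 has "Percentage change in MELD score from baseline to Day 28" and SAP 2.2 has "Percentage change in Model End-stage Liver Disease (MELD) score from baseline to Day 28".

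The sections that set up the test do not mention percent. Protocol 12.3 states the effect size of 0.54 "in MELD change from baseline with 80% power", and SAP 3 repeats this. Protocol 12.8.2 says: "The primary efficacy variable will be change in MELD score from baseline to Day 28". SAP 6.11 says: "The efficacy primary endpoint of the study is the change in MELD score from baseline to day 28". Its null hypothesis is one "of no difference in change from baseline to day 28 between those patients treated with 1000mg DS102 (BD) and placebo".

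SAP 6.11.1 then uses both terms: "Percentage change in MELD score from baseline up to and including day 28 will be assessed by modelling change from baseline", by MMRM on the full analysis set, with treatment, visit, their interaction and baseline MELD in the model. The output is the least squares means and their difference at Day 28, with a 95% CI and p-value. If normality fails, the model is refitted to change in log-transformed MELD; no back-transformation is given.

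Two further sections bear on the meaning. SAP 6.11.3 summarises absolute change and percentage change as separate quantities. SAP 6.12.8 takes the secondary endpoint, change in MELD at Days 7, 14 and 21, from the 6.11.1 model and prints it in the primary endpoint's table.

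**The concern.** A primary analysis has to fix its response variable before anyone sees treatment codes. Here two competent programmers could build different primary models, one in MELD points and one in percent, and each could cite the SAP. If the results differed near the 5% level, or one scale read better, the choice would be made with the data in view.

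There is also a gap in what is reported. The endpoint sections promise a conclusion in percent. If the model is in points, the primary test answers a different question, and no planned analysis compares mean percentage change between the arms.

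**Working it through.** **1. The plan's own figure.** Inputs from Protocol 12.3 and SAP 3: d = 0.54, two-sided alpha 0.05, 80% power, 1:1 allocation, two-sample t-test. The noncentral t distribution gives n = 54.8, so 55 per group. Power at 55 is 0.8014, as printed; at the 60 per group to be randomised it is 0.835. Since d is a difference divided by an SD, it carries no unit. The figure of 55 holds on whichever scale d refers to, but it does not tell us which scale that is.

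**2. Whether the word change could be shorthand for percentage change.** The SAP's own usage speaks against it. Section 2.2 lists percentage change as primary and change, at earlier visits, as secondary. Section 6.11.3 names absolute and percentage change side by side.

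**3. Each reading of SAP 6.11.1 set against the rest of the plan.**

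| Item | Response in points | Response in percent |
|---|---|---|
| Declared endpoint (synopsis, Protocol 5.1, SAP 2.2) | no match | match |
| Primary variable (Protocol 12.8.2, SAP 6.11) | match | no match |
| Null hypothesis (SAP 6.11) | match | no match |
| Secondary change in MELD from the same model (SAP 6.12.8) | match | no match |

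Points is the natural reading. On either reading, one declared endpoint is not analysed as declared.

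**4. What is left for mean percentage change if the response is in points.** SAP 6.11.3 gives summaries by arm and visit. Under SAP 6.1 these contain n, mean, SD, quartiles and range, with no CI and no comparison of arms. SAP 6.12.7 does test percentage change, but only cut at a 25% reduction, which is a different quantity from the mean.

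**5. The scales are not interchangeable.** Percentage change = 100 × change / baseline. The entry threshold is MELD 18 (Protocol 7.2); a baseline of 30 is assumed for contrast.
- 5-point fall from 18: 5/18 = 27.8%.
- 5-point fall from 30: 5/30 = 16.7%.

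**6. If d = 0.54 was meant in points but percent is chosen.** The documents give no SD and no target difference on either scale, so this is an illustration on assumed inputs:
- baseline MELD normal with mean 22 to 28 and SD 3 to 6, truncated to 18–40;
- SD of change 5 or 7 points, independent of baseline; mean placebo change −3;
- an effect either constant in points or proportional to baseline; no covariate adjustment.

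Under these inputs d on percentage change is about 0.51 to 0.53. Power at 55 per group is about 75% to 79%, and 80% power needs 56 to 62 per group.

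**The case against.** The strongest reply is that this is a matter of labels in an exploratory phase II trial. The analysis sections of both documents (Protocol 12.8.2, SAP 6.11) agree on change in MELD, and power and type I error may differ little between the scales. That stands as far as it goes: no inflation of error is claimed here. It does not settle what the primary test estimates, because SAP 6.11.1, the section a programmer will follow, names both scales.

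Four stronger readings are tempting, and the documents do not support them.

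- *Percentage change gets no estimate at all.* It does get one: SAP 6.11.3 with 6.1 gives the mean per arm and visit. What is missing, on the points reading, is the between-arm difference, CI and p-value.
- *The primary model is certainly in points.* SAP 6.12.8 favours this but does not settle it. The opening words of the 6.11.1 sentence can be read as making percentage change the response.
- *The SAP changed the scale and failed to record it in 6.25.* The conflict is already inside the protocol, 5.1 against 12.8.2. The SAP inherits it, so its absence from a list of departures from the protocol is not a separate fault.
- *The sample size is wrong, or is wholly unaffected.* Neither follows. It is correct for d = 0.54 on the chosen scale, and would need restating only if d was meant on the other one.

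One might also say that a point difference can be divided by mean baseline MELD. For a constant point effect under the baselines assumed above, that understates the mean percentage difference by only about 1% to 3%. But it is not a planned analysis, and it gives no CI or p-value for the declared endpoint.

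Nor does the log fallback reconcile the scales. It is relative, but it applies only if normality fails, and the plan does not say how its result would be expressed.

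**Conclusion.** The concern holds in this form: the scale of the primary endpoint is inconsistent across and within the two documents, and should be settled before unblinding. This rests on the wording alone and needs no assumed figure. Three places declare percent. Five (Protocol 12.3 and 12.8.2, SAP 3, SAP 6.11 and its null hypothesis) use change, and SAP 6.11.1 combines the two without a conversion.

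The arithmetic shows only that the distinction is material for a patient: the same 5 points is 27.8% at the entry threshold and 16.7% at an assumed MELD of 30. The possible fall in power, from 80% to about 75–79%, applies only if d = 0.54 was meant in points and percent is chosen. It comes from unadjusted calculations on assumed inputs, whereas the planned model adjusts for baseline, so it is not an estimate of the planned test's power.

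**What to change.** Before unblinding, name one scale and make it the MMRM response. Either choice is coherent.

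(a) *Absolute change in MELD points.* Correct the synopsis, Protocol 5.1, SAP 2.2 and the opening of SAP 6.11.1. Protocol 12.8.2, the SAP 6.11 hypothesis and SAP 6.12.8 can then stand, and percentage change remains a summary under SAP 6.11.3.

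(b) *Percentage change.* Make it the response in SAP 6.11.1, and align Protocol 12.8.2 and SAP 6.11 with its null hypothesis. Give SAP 6.12.8 its own model of absolute change. State in Protocol 12.3 and SAP 3 that d = 0.54 refers to percentage change; if it was meant in points, restate the power.

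In both cases, state how a result from the log-scale fallback would be back-transformed and reported.

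The cost is a SAP amendment, for which SAP 6.2 already provides a route before database lock, and a protocol amendment of the endpoint wording under (a) or of the analysis and sample size wording under (b). The protocol amendment goes to the authorities and ethics committees if judged substantial (Protocol 13.1). No new data or patients are needed, unless the sponsor chooses (b), finds that d was meant in points, and wishes to restore 80% power by enlarging the trial.
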